6. STUDY DRUG

6.1 IDENTITY OF PLECANATIDE AND PLACEBO

Plecanatide is a synthetic hexadecapeptide that is an analog (identical, with the exception of a single amino acid) of uroguanylin, a natural hormone. The chemical name, molecular formula, molecular weight, and amino acid sequence of plecanatide can be found in the IB provided to each clinical site.

The drug product is a tablet comprised of plecanatide, microcrystalline cellulose, and magnesium stearate. Matching placebo composition is identical but does not contain plecanatide. Both plecanatide and placebo tablets are manufactured by UPM Pharmaceuticals (Bristol, TN) and packaged by Sharp Packaging Solutions (Allentown, PA). Study supplies will be retested as required by the sponsor.

6.2 ADMINISTRATION

Study drug will be administered for 4 consecutive weeks according to the randomization scheme displayed in **Table 3**. Each patient will take one or two tablets (based upon randomization into Group A or B) orally (by mouth) daily preferably at the same time each day—**in the morning**—with approximately 240 mL (~8 oz.) of liquid, with or without food*.

Patients in treatment arms 1, 2, and 3 (Group A) will be dispensed one drug kit and take one tablet daily. Patients in treatment arms 4, 5, 6, and 7 (Group B) will be dispensed two drug kits and take two tablets daily (one tablet from each drug kit).

****For smaller children that are unable to swallow the plecanatide or placebo tablet, the parent/caregiver may crush the tablet into applesauce or water. Rescue medication (Dulcolax®) tablets are very small and coated so must be swallowed whole.***

No dose adjustments will be allowed on this study.

Table 3 Treatment Arms					
Treatment Arm (Age Dose Group)		Treatment	No. of Tablets to be Taken Daily	Dose Level	Number of Patients
1	(6 to 11 yrs. old)	0.5 mg plecanatide	1	0.5 mg plecanatide	30
2	(6 to 11 yrs. old)	1.0 mg plecanatide	1	1.0 mg plecanatide	30
3	(6 to 11 yrs. old)	Matching placebo	1	placebo	30
4	(12 to < 18 yrs. old)	0.5 mg plecanatide	2	1.0 mg plecanatide	30
5	(12 to < 18 yrs. old)	1.0 mg plecanatide	2	2.0 mg plecanatide	30
6	(12 to < 18 yrs. old)	1.5 mg plecanatide	2	3.0 mg plecanatide	30
7	(12 to < 18 yrs. old)	Matching placebo	2	placebo	30

6.2.1 Overdose

Plecanatide has minimal systemic absorption, therefore standard treatment measures for the symptomatology being exhibited should be provided. Notable, plecanatide was generally well-tolerated in adults after single doses up to 48.6 mg and multiple doses up to 9.0 mg for 12 weeks in prior studies.

6.3 STOPPING CRITERIA

Overall safety monitoring for the trial is the responsibility of the Medical Monitor (MM) who reviews adverse event listings and provides ongoing medical oversight of adverse event reports throughout the duration of the trial. Any interruption of study drug for an individual patient, or for the study, based on the established stopping criteria outlined below will be initiated by the Medical Monitor.

6.3.1 Individual Patient Stopping Criteria

Adverse events due to study drug that affect individual patient safety may necessitate dose interruptions or early discontinuation as described in this section.

Plecanatide therapy in adults with IBS-C and CIC has caused diarrhea in 4% and 5% of patients respectively, with severe diarrhea occurring in 0.7% and 0.6% of patients respectively. Severe diarrhea may cause dehydration. Pediatric patients may be at increased risk for diarrhea and dehydration with plecanatide therapy.

In general, study drug dosing should not be modified for mild diarrhea (Grade 1: increase of < 4 stools per day over baseline) or mild dehydration (Grade 1: dry mucous membranes, diminished skin turgor) (*National Cancer Institute, Common Terminology Criteria for Adverse Events [CTCAE] v5.0, November 27, 2017*). If study drug is not well tolerated by an individual patient, treatment will be permanently discontinued for that patient.

The following guidelines should be used in the case of moderate or severe diarrhea or dehydration:

Table 4 Individual Patient Stopping Criteria

Worst Observed Toxicity Grade NCI Common Toxicity Criteria	Dose Modification for Study Drug
Diarrhea	
Grade 2: Increase of 4-6 stools per day over baseline	No intervention required
Grade 3: Increase of ≥ 7 stools per day over baseline, incontinence, hospitalization indicated	Interrupt study drug for < 7 days until resolved to less than Grade 2 severity. If diarrhea was study drug-related, permanently discontinue study drug. If diarrhea was not study drug-related, e.g., viral gastroenteritis, then consider resuming treatment after consultation with Sponsor's Medical Monitor
Grade 4: Life-threatening consequences, urgent intervention indicated	Permanently discontinue study drug
Dehydration	
Grade 2: IV fluids indicated < 24 hour	Interrupt study drug for < 7 days until resolved to less than Grade 2 severity. If dehydration was study drug-related, permanently discontinue study drug. If dehydration was not study drug-related, consider resuming treatment after consultation with Sponsor's Medical Monitor
Grade 3: IV fluids or hospitalization indicated	Permanently discontinue study drug

Table 4 Individual Patient Stopping Criteria

Grade 4: Life-threatening consequences, urgent intervention indicated	Permanently discontinue study drug
---	------------------------------------

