6.3.2 Study Stopping Criteria

Dosing of all patients in the study will be interrupted for at least one week if ≥ 2 patients receiving study drug develop drug-related Grade 3 diarrhea and/or dehydration or if one patient develops drug-related Grade 4 diarrhea and/or dehydration. This will allow the Sponsor to assess whether the trial should be stopped or modified.

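### Table 4's dehydration Grade 2 row lies wholly inside its Grade 3 row, so one short IV-fluid event fits two rows whose consequences differ

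*Combined protocol and SAP*

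**What the plan says.** Protocol section 6.3.1 sets the individual stopping rules in Table 4, under the column heading "Worst Observed Toxicity Grade NCI Common Toxicity Criteria". For dehydration:

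- The Grade 2 row is "Grade 2: IV fluids indicated < 24 hour". Study drug is interrupted for less than a week while the event resolves. Two causality branches follow: "If dehydration was study drug-related, permanently discontinue study drug", and "If dehydration was not study drug-related, consider resuming treatment after consultation with Sponsor's Medical Monitor".
- The Grade 3 row is "Grade 3: IV fluids or hospitalization indicated". Study drug is stopped permanently, with no condition on causality.

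Section 6.3.2 interrupts dosing of all patients for at least one week if "≥ 2 patients receiving study drug develop drug-related Grade 3 diarrhea and/or dehydration", or if one patient has a drug-related Grade 4 event. Grade 2 events do not count.

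Section 6.3 makes the Medical Monitor responsible for initiating any interruption under these criteria, for one patient or for the whole study.

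**The concern.** A stopping rule should send each event to one action. Here the lower grade is limited to IV fluids for under 24 hours. The higher grade is met by IV fluids of any length, because hospitalization is joined to it by an or. A child who needs a few hours of IV fluid satisfies both rows.

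Two things are at stake: whether a child whose dehydration has another cause may resume study drug, and whether a drug-related event moves the trial toward a study-wide interruption. Section 6.3.1 itself says that children may be at increased risk of diarrhea and dehydration on plecanatide, so the ambiguity lies in the rule for a risk the protocol has singled out.

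**Working it through.** The documents state no operating characteristic for these rules, so there is no planned figure to reproduce. The check is one of logic.

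**Step 1: do the rows overlap?** Grade 2 is the set of events with IV fluids indicated for under 24 hours. Grade 3 is the set with IV fluids indicated for any duration, or hospitalization indicated. The first set is contained in the second, so the overlap covers all of Grade 2. By contrast, the stool-count ranges for diarrhea in section 6.3.1 (fewer than 4, 4 to 6, and 7 or more over baseline) do not overlap.

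**Step 2: what does the choice of row change?** Take one event with IV fluids for under 24 hours and hold causality fixed.

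| Causality | Row used | Action for the child | Counts toward 6.3.2 |
|---|---|---|---|
| Drug-related | Grade 2 | Permanent discontinuation | No |
| Drug-related | Grade 3 | Permanent discontinuation | Yes |
| Not drug-related | Grade 2 | Interruption; resumption may be considered | No |
| Not drug-related | Grade 3 | Permanent discontinuation | No |

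Within each causality branch the row changes exactly one thing: the study-level count if related, the individual action if not.

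**Step 3: is there a boundary elsewhere?** None was found.

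- Section 7.3.2 grades intensity as mild, moderate or severe. It does not mention IV fluids and does not map to Table 4.
- Section 6.3.1 cites CTCAE v5.0 beside the Grade 1 descriptions, but the wording of those criteria is not in the documents and is not used here.
- SAP section 5.3.2 names version 4.03, for laboratory toxicities.

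**Step 4: how sensitive is the study-level rule?** Two short drug-related IV-fluid episodes in two patients contribute 0 under the Grade 2 reading and 2 under the Grade 3 reading, and 2 meets the threshold.

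The following is an illustration only. Let n be the patients at risk and p the chance that a patient has a counted event. Then P(at least 2) = 1 − (1 − p)^n − n·p·(1 − p)^(n−1). Assumptions:

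- n = 150, from five plecanatide arms of 30 in Table 3.
- A base rate of 0.7%, borrowed from the adult IBS-C severe-diarrhea figure in section 6.3.1.
- An extra 0.25% to 2% of patients with short-IV-fluid, drug-related dehydration. The documents give no such rate.

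If the short episodes are Grade 2, p = 0.007. Then (0.993)^150 = 0.349 and 150 × 0.007 × (0.993)^149 = 0.369, so P = 1 − 0.349 − 0.369 = 0.28.

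If they are Grade 3:

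| Extra rate | p | P(at least 2) |
|---|---|---|
| 0.25% | 0.0095 | 0.42 |
| 0.5% | 0.012 | 0.54 |
| 1% | 0.017 | 0.73 |
| 2% | 0.027 | 0.92 |

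Section 2.1.5 gives 1.0% for adult severe diarrhea in IBS-C. With that base, 0.44 rises to between 0.56 and 0.94. These values show that the trigger is sensitive to the grading. They do not estimate what would happen in this trial.

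**The case against.** The strongest reply has three parts.

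**The natural reading is a rising scale.** Grade 2 carries an explicit time limit, so a clinician would probably take Grade 3 to begin where that limit ends. The defect may be no more than a missing qualifier. That is plausible, but the qualifier is not written, and the actions depend on it.

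**The heading breaks the tie.** If "Worst Observed Toxicity Grade NCI Common Toxicity Criteria" means that a double match goes to the higher grade, every event has one row. The Grade 2 row then never applies, and its instruction on considering resumption has no use. If the heading means only the peak grade during an event, it does not settle the overlap. Neither reading makes both rows work.

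**One central role applies the table.** The Medical Monitor initiates interruptions, and resumption after a Grade 2 event needs consultation with the same role. This stands as a real limit on variation: a reader might infer that two sites would routinely treat the same event in opposite ways, and section 6.3 does not support that. It does not, however, give the Medical Monitor a written boundary to apply.

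A reader might also infer that a single event can lead either to possible resumption or to permanent discontinuation plus a count toward the study-wide interruption. It cannot. Resumption is open only to unrelated events, which never count. Related events count only at Grade 3 or above, and they end in permanent discontinuation under both rows.

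**Conclusion.** The concern holds as a drafting contradiction in a pediatric safety rule. All Grade 2 dehydration events as defined also meet Grade 3. The row used decides the individual action for unrelated events and the section 6.3.2 count for related ones. This rests on the printed definitions alone and on no assumed rate.

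Two larger claims are not supported:

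- **Size of the problem.** A reader might take 2/150 = 1.3% of planned plecanatide patients as its size. That is only the threshold of the study-wide rule expressed as a proportion. It says nothing about how often short IV-fluid dehydration would occur, and the denominator would differ if placebo patients are regarded as receiving study drug.
- **Effect on the primary endpoint.** A reader might infer bias, because section 8.4.1 sets weekly SBM rates to 0 when no BM data are recorded. Table 4 stops study drug and does not say that the child leaves the study. The zeros apply only to weeks with no recorded response, and no number of affected children can be derived. No material effect on the primary analysis is shown.

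**What to change.** The sponsor's medical lead should reconcile the two dehydration rows in Table 4 so that each IV-fluid event falls in exactly one grade. Section 6.3.2 should state that its Grade 3 and Grade 4 events are those defined in Table 4, so that the individual and study-level rules use the same definitions. Where the boundary lies is a clinical decision, and this review does not propose one.

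The cost is a short protocol amendment and a notice to sites and the Medical Monitor. No procedures, visits or patients are added, and the SAP analyses do not change.

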6.3.2 Study Stopping Criteria

Dosing of all patients in the study will be interrupted for at least one week if ≥ 2 patients receiving study drug develop drug-related Grade 3 diarrhea and/or dehydration or if one patient develops drug-related Grade 4 diarrhea and/or dehydration. This will allow the Sponsor to assess whether the trial should be stopped or modified.

6.4 PACKAGING, LABELING AND STORAGE

All study centers will be provided with adequate supplies of study medication—plecanatide tablets at 3 tablet strengths (see **Table 3**) and identically appearing placebo tablets, by [REDACTED].

6.4.1 Packaging

Each investigational drug kit will be supplied in blister packaging. At the randomization visit (Day 1), eligible patients enrolled in treatment group A (6 to 11 years old) will receive one drug kit for the entire 4 weeks of dosing (Weeks 1, 2, 3, and 4) 28 days plus 4 additional tablets to allow for a +3-day window. Patients in treatment group B (12 to < 18 years old) will receive two drug kits and will be instructed to take one tablet from each drug kit (2 tablets daily) for the entire 4 weeks of dosing (56 tablets) plus 8 additional tablets to allow for a +3-day window. Patients will be instructed to bring their kits to the EOT or EW study visit for determination of compliance and reconciliation of supplies.

Each investigational study drug kit will contain 32 tablets. Individually blister-packaged tablets will be provided in four connected strips (of 8 tablets) as a 4-panel key-pack that folds into a carton. The two bottom panels fold up into the two top panels, nesting blister cavities. Instructions for releasing a tablet from the blister dome are printed on the outside of the carton.

Clinical sites will save all empty packaging or packaging containing unused tablets for final disposition instructions from the sponsor.

6.4.2 Label

Each of the investigational drug kits will have a unique label containing the following information: protocol number, drug kit number, contents, directions for use, storage conditions, Sponsor name, city, state, and zip code, and the statements: “Caution: New Drug — Limited by Federal Law to Investigational use. Investigational Drug – To be used by Qualified Investigator Only. For Clinical Trial Use Only. Keep Out of Reach of Children under 6 years”.

The label will include the following fields to be completed by site personnel: Investigator name and phone number, patient number, initials, and treatment weeks. When dispensing kit(s) to a patient, complete and remove the tear off portion of the label and keep this with the source documents. At each monitoring visit, the source document records will be verified against the IWRS assignment.

There will also be a smaller label on the carton spine that identifies the study number and drug kit number and Sponsor.

6.4.3 Storage

The Investigator, or qualified designee, is responsible for the proper storage of the study medications according to the Sponsor's recommendations and all applicable federal/state regulatory guidelines. At the clinical site, plecanatide should be stored at controlled room temperature 20°C to 25°C (68°F to 77°F) in a secure area with Min / Max Temperature Recording with restricted access. Deviations from Sponsors recommendations / guidelines should be reported, as directed in the Site Level Temperature Excursion Reporting Form.

Patients will be instructed to store their study drug at room temperature defined for this study as 20°C to 25°C (68°F to 77°F).

The Investigator must agree not to dispense or store the investigational drug at any location other than that listed on the Form FDA 1572.

6.5 BLINDING AND BREAKING THE BLIND

The study will be performed in a double-blind manner. All study drugs will be supplied in identical blister packs and tablets will be similar in color, smell, taste, and appearance, thereby assuring double-blind conditions.

In the event of a need to break the blind, the Investigator at the clinical site will have the ability to break the treatment code using the IWRS. The blind should only be broken following discussion on a case-by-case basis, with the Sponsor/Medical Monitor (except in a medical emergency). The Sponsor's Medical Monitor will also be granted emergency code-break privileges using the IWRS. All un-blinding events will be documented. The Sponsor and CRO, as applicable, will specify who in each company is able to review unblinded treatment in a blinded trial.

In the event of a treatment code-break, the time, date, reason, name, and signature of the person responsible for breaking the code must be fully documented in the patient's source documents and any associated AE recorded. The breaking of the blind will result in the withdrawal of the patient from study participation, and the patient should follow the procedures detailed for Early Withdrawal Visit study assessment (see **Section 5.2.8**).

The overall randomization code for the study will be broken at study completion. This will occur once all final clinical data have been entered into the database, data queries have been resolved, and the assignment of patients to the analysis sets has been completed.

6.6 DRUG ACCOUNTABILITY

Acknowledgement of receipt of drug shipments and distribution of all investigational drug kits will be recorded using the IWRS. The drug inventory log can be generated from IWRS at the site level as a standard report.

In addition, accurate records of study drug dispensed to patients will be kept by the Investigator, or qualified designee in IWRS, specifying the kit number, the patient number assigned, the amount dispensed to each patient, and the date dispensed. This information will be available in the IWRS for the overall study. At Visit 3 (EOT) or EW, the patient is asked to return their previously dispensed drug kit and the number of remaining tablets is entered into the IWRS for drug accountability.

A drug accountability log can also be generated from IWRS and must be available for inspection at each monitoring visit and at the completion of the study. At the completion of the study, the Investigator will provide signed copies of this accountability log to the Sponsor.

The Investigator is responsible for the retrieval of all study supplies from patients. At the completion of the study, all unused investigational drug kits will be returned to a third party in accordance with the Sponsor's (or designee's) written instructions. The Investigator must verify that all unused or partially used study drug supplies have been returned by the patient and that no remaining supplies are in the Investigator's possession.

6.7 COMPLIANCE

Patients will be advised as to how to take their daily medication and will return all unused study drug to the clinical site at the end of the Treatment Period or Early Withdrawal Visit. The number of remaining tablets will be counted and entered into IWRS for that patient. Patients unwilling or unable to maintain compliance with study drug administration or procedures may be discontinued from the study at the discretion of the investigator in conjunction with the medical monitor.

7. ASSESSMENT, REPORTING, RECORDING AND FOLLOW UP OF ADVERSE EVENTS

7.1 DEFINITION

An AE is any untoward medical occurrence associated with the use of a drug in humans, whether or not considered to be drug related. An AE can therefore be any unfavorable and unintended sign (including abnormal laboratory finding), symptom, or disease temporally associated with the use of an investigational product or study procedure whether or not considered related to the product or procedure.

NOTE: Specific gastrointestinal symptoms related to IBS-C are recorded daily in the electronic Diary in response to standardized questions and are BOTH efficacy AND safety response variables. These symptoms are abdominal pain, abdominal discomfort, and pain with defecation. The diary is a “real-time” patient reported outcome record that is based on “within 24 hours” patient recall. Because these symptoms are considered adequately recorded in the IBS-C Symptom Diary, they should generally not also be reported in the adverse event database that relies on a much longer patient recall period. To prevent double-recording of a single specific event, the daily IBS-C Symptom Diary record is considered the highest quality record of an event and should therefore be the only record of the same event.

All AEs, including intercurrent illnesses and regardless of the source of identification (e.g., physical examination, laboratory assessment, reported by patient), occurring during the study will be documented in the eCRF. Concomitant illnesses that existed before entry into the study will not be considered AEs unless they worsen during the treatment period.

Adverse events occurring from the time of signing the informed consent form (ICF) up to the intake of the first dose of study medication will be classified as pre-existing conditions for the study and therefore will be recorded in the Medical History page of the electronic case report form (eCRF). Serious adverse events (as defined below) occurring after the signing of informed consent but before randomization (i.e., during screening) will be collected and reported as such. A treatment emergent adverse event (TEAE) is defined as an AE that begins or worsens in frequency and/or severity after at least one dose of study drug has been administered.

Minor fluctuations in laboratory values for standard monitoring (abnormal values) that the investigator does not consider clinically significant or related to study drug will not be recorded as AEs. However, if the laboratory abnormality is associated with a diagnosis, then the AE term for that diagnosis will be reported.

7.2 EVENT REPORTS OF SPECIAL INTEREST – INCREASE IN BM FREQUENCY AND LOOSENING OF STOOL CONSISTENCY

An increase in the frequency of BMs and loosening of the stool consistency from baseline are expected pharmacodynamic effects of plecanatide. These same attributes (increased stool frequency and looser stool consistency) are often used to define “diarrhea”, however, in light of significant inter-patient variability in bowel habit “phenotype” and wide differences in the perception of a “normal” bowel habit there is no standard definition of “diarrhea” for this patient population. An increase in frequency or consistency for one person is a welcome event while for another patient it might be bothersome “diarrhea”. In all cases, as mentioned in the NOTE above, the frequency and consistency of each bowel movement is recorded in the electronic diary. However, this objective record often does not go far enough to characterize any change in bowel frequency or consistency as clinically important or impactful for the patient (whether beneficial or harmful).

One mechanism to introduce a level of consistency across patients, sites and the trial is to code an event as diarrhea only if it is characterized by a specific patient-reported and clinically relevant attribute such as “bothersomeness”. Therefore, for this trial, for any event associated with a significant increase from baseline in BM frequency and/or loosening of BM consistency - that would otherwise be coded as diarrhea

- the site is instructed to record it as an AE only if the patient reports that it was bothersome (as defined by each patient). Sites may question the patient/caregiver to ascertain whether or not they thought their diarrhea was bothersome.

